Visit*	Treatment Cycle 1 (Infusions 1-3)										Treatment Cycle 2 / Treatment Cycle 3 (Infusions 4-9)			Treatment Cycle 4 (Infusions 10)			SV / FE	Total Number of Samples																			
	Day 0	Day 1 (Inf. 1)		Day 2 to Day 4		Day 8 (Inf. 2)	Day 15 (Inf. 3)	Day 1 (Inf. 4/7)	Day 8 (Inf. 5/8)	Day 15 (Inf. 6/9)	Day 1 (Inf. 10)		Day 2 to Day 4		Day 8																						
	W1					W2	W3	W4/ W7	W5/ W8	W6/ W9	W10		W11		W12																						
Timing	Prior infusion	0 h	Prior infusion		At end of inf.		After start of inf.		After start of inf.		Prior infusion (168 ± 2 h after start of 1 st infusion on Day 1)		0 h	Prior infusion		At end of inf.		Prior infusion		At end of inf.		At end of inf.		At end of inf.		At end of inf.		At end of inf.		After start of inf.		After start of inf.		Prior inf. (168 ± 2 h after start of 10 th infusion)		28 days after last inf.	
	0 h	0 h	5 h ± 5 min	7 h ± 15 min	24 ± 1 h	48 ± 2 h	72 ± 2 h	0 h	0 h	0 h	0 h	0 h	0 h	0 h	0 h	0 h	0 h	0 h	5 h ± 5 min	7 h ± 15 min	24 ± 1 h	48 ± 2 h	72 ± 2 h	0 h	5 h ± 5 min	7 h ± 15 min	24 ± 1 h	48 ± 2 h	72 ± 2 h	0 h	5 h ± 5 min	7 h ± 15 min	24 ± 1 h	48 ± 2 h	72 ± 2 h		
All Patients (CetuGEX™ arm)	X	X	X	X						X	X	X	X	X	X	X	X	X																		X	23
Selected Subset					X	X	X	X	X										X	X	X	X	X	X													11

If the administration of CetuGEX™/cetuximab is skipped for any reason, the pre-dose blood sample scheduled for this study visit day is to be taken as planned.

* In case of premature discontinuation of chemotherapy cycles, please refer to the corresponding CetuGEX™ infusion numbers for scheduling PK assessments.

W = Week

C. Response Evaluation Criteria in Solid Tumors

The criteria below are based on RECIST 1.1 criteria as described by Eisenhauer et al. (2009) and adapted according to immune-related response criteria (irRC) as defined by Wolchok et al. (2009). The adapted immune-related RECIST 1.1 (modified irRC) criteria are used in order to permit physicians to continue treatment in spite of the appearance of small new lesions and/or transient increases in tumor burden, as these may be manifestations of an anti-tumoral inflammatory response in a therapeutic setting which involves immunological mechanism of action.

Measurable Lesions:

The tumor lesion must be accurately measured in at least one dimension (longest diameter in the plane of measurement will be recorded) with a minimum size of:

- 10 mm by CT scan (CT scan slice thickness no greater than 5 mm)
- 20 mm by chest x-ray

Measurable malignant lymph node:

To be considered pathologically enlarged and measurable, a lymph node must be at least 15 mm in short axis when assessed by CT/MRI scan (CT/MRI scan slice thickness recommended to be no greater than 5 mm). At baseline and in follow-up, only the short axis will be measured and followed. Nodes with a short axis >10 and <15 mm will be considered pathologically enlarged but non-measurable (see below).

Lytic bone lesions or mixed lytic-blastic lesions with identifiable soft-tissue components will be considered measurable if the soft-tissue component can be evaluated by cross-sectional imaging (i.e., CT scan) and meets the general definition of measurability.

A lesion located in a previously irradiated area, or an area previously subjected to any locoregional therapy, will be considered measurable only if there has been a documented increase in lesion size subsequent to prior treatment but before study entry.

Non-Measurable Lesions

Non-measurable lesions are all other lesions, including small lesions (longest diameter smaller than 10 mm or pathological lymph nodes with ≥ 10 to < 15 mm short axis) as well as truly non-measurable lesions. Lesions considered truly non-measurable are: leptomeningeal disease, ascites, pleural or pericardial effusion, inflammatory breast disease, lymphangitic involvement of skin or lung, abdominal masses/abdominal organomegaly identified by physical exam that is not measurable by reproducible imaging techniques.

Simple cysts will not be considered malignant lesions, and will be neither measurable nor non-measurable. Cystic lesions believed to be metastases may be considered measurable if they meet the general definition of measurability, but non-cystic lesions are preferred as target lesions.

New Lesions

The definition of measurable and non-measurable lesions also applies to new lesions to be included in the assessments for adapted immune-related RECIST 1.1.

Methods of Measurement

All measurements must be recorded in metric notation, using a ruler or calipers. All baseline evaluations must be performed as close as possible to the treatment start and never more than 4 weeks before the beginning of the treatment.

The same method of assessment and the same technique must be used to characterize each identified and reported lesion at baseline and during follow-up. Imaging based evaluations should always be done rather than clinical examination unless the lesion(s) being followed cannot be imaged but are assessable by clinical exam.

Clinical lesions will only be considered measurable when they are superficial and at least 10 mm as assessed using calipers (e.g., skin nodules, palpable lymph nodes). In the case of skin lesions, documentation by color photography including a ruler to estimate the size of the lesion is suggested.

Lesions on chest x-ray may be considered measurable if they are clearly defined and surrounded by aerated lung. However, CT scan is preferred.

CT scans and MRI are the best currently available and reproducible methods to measure lesions selected for response assessment.

Ultrasound is not useful in assessment of lesion size and should not be used as a method of measurement. Ultrasound examinations cannot be reproduced in their entirety for independent review at a later date and, because they are operator dependent, it cannot be guaranteed that the same technique and measurements will be taken from one assessment to the next.

Endoscopy and laparoscopy: the use of these techniques for objective tumor evaluation is not advised. However, they can be useful to confirm complete pathological response when biopsies are obtained.

Tumor markers alone cannot be used to assess response. If markers are initially above the upper normal limit, they must normalize for a patient to be considered in complete clinical response.

Cytology and histology can be used to differentiate between PR and CR in rare cases (for example, residual lesions in tumor types such as germ cell tumors, where known residual benign tumors can remain).

Baseline Documentation of Target and Non-Target Lesions

When more than 1 measurable lesion is present at baseline all lesions up to a maximum of 5 lesions total (and a maximum of 2 lesions per organ) representative of all involved organs should be identified as target lesions and will be recorded and measured at baseline (this means in instances where patients have only 1 or 2 organ sites involved a maximum of 2 and 4 lesions respectively will be recorded).

Target lesions should be selected on basis of their size (lesions with the longest diameter), be representative of all involved organs, but in addition should be those that lend themselves to reproducible repeated measurements.

Lymph nodes merit special attention since they are normal anatomical structures which may be visible by imaging even if not involved by tumor. As previously mentioned, pathological nodes defined as measurable must meet the criterion of a short axis of at least 15 mm by CT/MRI scan to be identified as target lesions. Only the short axis of these nodes will contribute to the baseline sum. All other pathological nodes (those with short axis ≥ 10 mm but < 15 mm) should be considered non-target lesions. Nodes that have a short axis less than 10 mm are considered non-pathological and should not be recorded or followed.

A sum of the diameters (longest for non-nodal lesions, short axis for nodal lesions) for all target lesions will be calculated and reported as the baseline sum diameters. The baseline sum diameters will be used as reference to further characterize the objective tumor response.

All other lesions (or sites of disease) including pathological lymph nodes should be identified as non-target lesions and should also be recorded at baseline. Measurements are not required but the presence or absence of each should be noted throughout follow-up.

Response Criteria According to Adapted Immune-Related RECIST 1.1

In this study, disease progression using adapted immune-related RECIST 1.1 as determined by the investigator will serve to determine discontinuation from study treatment. New lesions will be measured and incorporated into the tumor assessment. Tumor diameter will be treated as a continuous variable and new lesion diameter will be added to the diameter of existing target diameter sum.

The response assessment in this study is based on total measurable tumor burden adapted from Wolchok et al. (2009). Selected target lesions and measurable new lesions occurring after start of study treatment are incorporated into the tumor burden. Up to 2 measurable new lesions per organ are added together with the sum of diameters of the target lesions to provide the total tumor burden.

Evaluation of target lesions

1. Complete Response (CR): Disappearance of all non-nodal target lesions. Any pathological lymph nodes (whether target or non-target) must have reduction in short axis to < 10 mm.
2. Partial Response (PR): At least a 30% decrease in the tumor burden (sum of the longest lesion diameter (LD) of target lesions (including the short axes of any target lymph nodes plus measurable new lesions), taking as reference the baseline sum diameters.
3. Progressive Disease (PD): At least a 20% increase in the tumor burden (including the short axes of any target lymph nodes plus measurable new lesions), taking as reference the smallest tumor burden recorded since the treatment started.

4. Stable Disease (SD): Neither sufficient shrinkage to qualify for PR nor sufficient increase to qualify for PD, taking as reference the smallest tumor burden since the treatment started.

Evaluation of non-target lesions

1. Complete Response (CR): Disappearance of all non-target lesions and normalization of tumor marker level. All lymph nodes must be non-pathological in size (< 10 mm short axis).
2. Non-CR/Non-Progressive Disease (-PD): Persistence of one or more non-target lesions.
3. PD: Unequivocal progression of existing non-target lesions. To achieve “unequivocal PD”, there must be an overall level of substantial worsening in non-target disease that is of a magnitude that, even in the presence of SD or PR in target lesion, the treating physician would feel it important to change therapy.

Although a clear progression of “non-target” lesions only is exceptional, in such circumstances, the opinion of the treating physician should prevail, and the progression status should be confirmed at a later time by the review panel (or study chair).

Evaluation of Best Overall Response According to Adapted Immune-Related RECIST 1.1

The best overall response is the best response recorded from the start of the treatment until disease progression/recurrence (taking as reference for PD the smallest measurements recorded since the treatment started). The patient's best response assignment will depend on the achievement of measurement criteria.

Measurable response	Non-measurable response		Overall Response
Target and new, measurable lesions (tumor burden), %	Non-target lesions	New, non-measurable lesions	Using irRECIST
↓100	CR	Absent	irCR
↓100	Stable	Any	irPR
↓100	Unequivocal progression	Any	irPD
↓≥30*	Absent/Stable	Any	irPR
↓≥30*	Unequivocal progression	Any	irPD
↓<30 to <20↑	Absent/Stable	Any	irSD
↓<30 to <20↑	Unequivocal progression	Any	irPD
≥20	Any	Any	irPD

*Decrease assessed relative to baseline, including measurable lesions only (≥10mm longest diameter).

Duration of Response

Duration of Overall Response

The duration of overall response is measured from the time measurement criteria are met for CR or PR (whichever is first recorded) until the first date that recurrent or PD is objectively documented (taking as reference for progressive disease the smallest measurements recorded since the treatment started).

The duration of overall CR is measured from the time measurement criteria are first met for CR until the first date that recurrent disease is objectively documented.

Duration of Stable Disease

Stable disease is measured from the start of the treatment until the criteria for progression are met, taking as reference the smallest measurements recorded since the treatment started.

D. Regulations and Good Clinical Practice Guidelines

1. Regulations

Refer to the following United States Code of Federal Regulations (CFR) and European Directives:

- FDA Regulations 21 CFR, Parts 50.2 – 50.27
Subpart B – Informed Consent of Human Subjects
- FDA Regulations 21 CFR, Parts 56.107 – 56.115
Part 56 – Institutional Review Boards
Subpart B – Organization and Personal
Subpart C – IRB Functions and Operations
Subpart D – Records and Reports
- FDA Regulations 21 CFR, Parts 312.50 – 312.70
Subpart D – Responsibilities of Sponsors and Investigators
- European Directive 2001/20/EC and related guidance documents
- Relevant local laws and regulations

2. Good Clinical Practice Guidelines

ICH GCP guidelines can be found at the following URL:

<http://www.ich.org/LOB/media/MEDIA482.pdf>

E. SmPC for Cetuximab (Erbitux®)

(An English version and a version translated to local language of the SmPC will be attached as separate documents.)

F. SmPC for Cisplatin

(An English version and a version translated to local language of the SmPC will be attached as separate documents.)

G. SmPC for 5-FU

(An English version and a version translated to local language of the SmPC will be attached as separate documents.)

H. SmPC for Carboplatin

(An English version and a version translated to local language of the SmPC will be attached as separate documents.)

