10.3.1.2 Assessment of Secondary Efficacy Endpoints

Tumor assessments performed by the investigator and by independent centralized reading as described in detail above will also be used for evaluation of secondary efficacy endpoints.

Progression-free Survival assessed by Centralized Read

Tumor images to determine PFS as assessed by independent centralized reading will be evaluated as described in detail in Section 10.3.1.1.

Objective Response Rate and Duration of Response

Objective response rate is the portion of patients with a tumor size reduction of a predefined amount for a minimum time period and it is defined as the sum of partial responses and complete responses. Response duration is measured from the time of initial response until documented tumor progression.

The investigator and independent centralized reader will evaluate whether complete response (CR), partial response (PR), stable disease (SD) or progressive disease (PD) has occurred, according to the criteria presented in Appendix C:

Best Overall Response Rate

The best overall response rate is the best response (CR, PR or SD) recorded per patient from the start of the treatment until disease progression/recurrence. Separate rates per CR, PR or SD as best response will be evaluated.

Clinical Benefit Rate

The clinical benefit rate is the portion of patients with an objective response or stable disease.

Overall Survival

The overall survival is defined as the duration of time from randomization to the time of death. The patients will be followed up by monthly phone calls until death or for a maximum duration of 24 months after randomization of the last patient for assessment of OS.

Time to Treatment Failure

Time to treatment failure is defined as the time from randomization to treatment discontinuation for any reason, including disease progression, treatment toxicity, patient preference, or death.

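### Protocol Appendix C: a patient who meets the CR definition but keeps a target node above 0 and below 10 mm is CR by the text and irPR by the overall-response table

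*Protocol*

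**What the plan says.** All the rules sit in Protocol Appendix C.

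- **CR definition, target lesions.** Non-nodal targets must disappear. For nodes the requirement is weaker: "Any pathological lymph nodes (whether target or non-target) must have reduction in short axis to < 10 mm". The non-target CR rule sets the same 10 mm limit for lymph nodes.
- **Entry of nodes as targets.** To count as measurable, "a lymph node must be at least 15 mm in short axis when assessed by CT/MRI scan". For such target nodes, "Only the short axis of these nodes will contribute to the baseline sum".
- **Follow-up.** For nodes, "At baseline and in follow-up, only the short axis will be measured and followed". The burden used for PR and PD is described as "including the short axes of any target lymph nodes plus measurable new lesions".
- **Overall-response table.** The first column is headed "Target and new, measurable lesions (tumor burden" and is expressed as a percent change. The only irCR row requires ↓100, with non-target CR and no new non-measurable lesions. A fall of at least 30, with non-target lesions absent or stable, is irPR.

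On reporting, Protocol section 10.3.1.2 says "Separate rates per CR, PR or SD as best response will be evaluated". SAP section 2.2.1 lists best overall response by category as a secondary endpoint, SAP section 7.2 defines duration of CR, and SAP section 11.1 cross-tabulates investigator and central best response under irRC.

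**The concern.** The CR definition accepts that a normalized lymph node can remain visible. The table does not, because it asks for a zero sum and the sum contains that node. The two rules cannot both be applied to a patient whose tumor has otherwise gone and whose target node has shrunk to a normal size.

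What is at stake is the classification of some responders as CR or PR. An investigator may follow the definition and the central reader the table, or the reverse. The SAP 11.1 cross-table would then show a disagreement that comes from the appendix and not from the images. SAP section 9.1 already records that sites were not uniform in applying modified irRC, and the trial is open label, so an undefined choice at this point is better removed.

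**Working it through.** The plan states no figure on this point, so there is nothing to reproduce. The check applies the Appendix C rules directly.

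**Inputs (all Appendix C).** A target node is at least 15 mm in short axis at baseline. CR allows it to be under 10 mm. Target-node short axes are in the baseline sum and in the follow-up burden. irCR needs a fall of 100%; irPR needs a fall of at least 30% with non-target lesions absent or stable.

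**Formula.** Fall (%) = 100 × (1 − follow-up burden / baseline burden). Assume non-nodal targets at 0 mm, no measurable new lesions, non-target CR and no new non-measurable lesions.

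| Case | Baseline → follow-up (mm) | Fall | CR definition | Table |
|---|---|---|---|---|
| Node 24→8, lung lesion 20→0 | 44 → 8 | 36/44 = 82% | CR | irPR |
| Node 20→8 only | 20 → 8 | 12/20 = 60% | CR | irPR |
| Node 20→8, mass 40→0 | 60 → 8 | 52/60 = 86.7% | CR | irPR |
| Two nodes, each 15→9.9 | 30 → 19.8 | 10.2/30 = 34% | CR | irPR |
| Node 20→0 only | 20 → 0 | 100% | CR | irCR |
| Node 20→12 only | 20 → 12 | 8/20 = 40% | not CR | irPR |

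**General bound.** Take k target nodes, each at least 15 mm at baseline and under 10 mm now, with at least one above 0. The follow-up burden is above 0 and below 10k, and the baseline burden is at least 15k. The fall is therefore above 100 × (1 − 10/15) = 33.3% and below 100%. Non-nodal targets that have disappeared only raise the baseline sum and so the fall. Every such patient clears the 30% threshold and misses 100%, so the table always gives irPR, never irCR and never irSD.

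**Which outputs move.** ORR pools CR and PR, and CBR pools CR, PR and SD, so a move between CR and PR changes neither. Duration of response starts at the first CR or PR and is also unchanged. PD is a rise of at least 20% from the smallest burden, or unequivocal non-target progression, and does not use the irCR row, so PFS is unchanged. The outputs that move are the CR and PR frequencies, the duration of CR, and the irRC cross-table.

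**The case against.** The best defence is that Appendix C already takes small nodes out of the sum. It says that nodes under 10 mm in short axis are non-pathological and are not to be recorded or followed. It bases response on measurable burden, and a measurable node is at least 15 mm. The table footnote reads "Decrease assessed relative to baseline, including measurable lesions only (≥10mm longest diameter". On that reading the 8 mm node drops out, the sum is zero and the patient is irCR, with ↓100 serving as shorthand for the written definition.

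This reading is possible but not secure:

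- The sentence on nodes under 10 mm stands in the text on baseline documentation, and the follow-up rule has target nodes measured throughout.
- The footnote is attached to the ≥30 rows and not to the ↓100 rows. It speaks of longest diameter, whereas nodes are judged by short axis.
- Read as a general rule, the footnote would also drop a non-nodal target that is still present but under 10 mm, against the requirement that such lesions disappear.
- Dropping every node under 15 mm as non-measurable would turn the 20→12 mm case into a 100% fall, although that node fails the CR definition.

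Other parts of the objection stand. The independent review charter, which the SAP cites for modified irRC, is not available here and may settle the central read. CR frequencies and duration of CR are only described; the response tests in SAP section 9.2.2 are on ORR and CBR. The central RECIST 1.1 results are reported separately from the irRC table.

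A reader might infer that patients with nodal targets are generally denied CR. The documents do not support that: a node that vanishes is irCR under both rules, and a node still at 10 mm or more is CR under neither. Nor do they support a bias between arms, since the same text governs both.

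**Conclusion.** The contradiction is real, and it is confined to patients who meet the CR definition with at least one target node above 0 and below 10 mm. For them the definition gives CR and the table gives irPR in every case. No sentence in the appendix clearly says which prevails.

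The consequence is limited to descriptive secondary outputs under modified irRC. No hypothesis test, sample-size figure or decision rule depends on the CR/PR split.

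The number of patients affected cannot be computed. If a share s of patients who meet the CR definition keep a residual target node, and a proportion p of those are scored by the table, the CR count falls by the factor s × p. The documents give neither quantity and no expected CR rate, so any specific loss in the CR rate would rest wholly on assumption. The conclusion assumes that target-node short axes stay in the follow-up burden, as the appendix states, and that the charter does not already set a different rule for the central read.

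**What to change.** In the irCR row, and in the other two ↓100 rows for consistency, replace ↓100 by: all non-nodal target and measurable new lesions absent, and all target nodes below 10 mm in short axis. These rows should be read before the ≥30 rows, since an affected patient also satisfies the 30% threshold.

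Leave the tumor-burden sums used for PR and PD as they are. Setting small nodes to zero is not an equivalent repair, because it lowers the nadir. For example, take a 20 mm mass and an 8 mm node at nadir, later 22 mm and 10 mm. With the node counted, 28→32 is a rise of 4/28 = 14%, which is not PD. With it zeroed at nadir, 20→32 is a rise of 12/20 = 60%, which is PD. That route would touch PFS; the row change does not.

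Check that the review charter states the same rule. For assessments already recorded, identify patients whose non-nodal targets and measurable new lesions are absent and whose target nodes are all below 10 mm with at least one above 0, and query the recorded category against the rule. Do not overwrite it with a programmed response, because SAP section 7.2 takes best response from the investigator's or central reader's classification.

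The cost is an amendment to three rows of the appendix table (Protocol section 14.7 requires a formal amendment), a charter check and a set of queries. The target-lesion measurements are already collected and planned for listing for both assessors (SAP section 15.2), so no new data are needed.
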